### 3.2 Safety Endpoints

Safety assessments will include physical examination (including heart murmurs), vital signs, electrocardiograms (ECGs), extensive cardiac monitoring including telemetry, adverse events (AEs), and clinical laboratory tests (including hematology, serum chemistry, coagulation, and urinalysis).

Female subjects will have blood collected for serum pregnancy testing. Females claiming postmenopausal status will have blood collected to measure follicle stimulating hormone (FSH) levels.

## 4 SAMPLE SIZE

For Part 1, 7 dose levels are planned. For 7 dose levels, 7 cohorts of 8 subjects will be used, 6 to receive active drug and 2 to receive placebo, all under fasting conditions.

QMD Ref: Worldwide-TMP-ST-006-4.0 Effective: 12Aug2019	Governing QMD: Worldwide-SOP-ST-001
Confidentiality Statement	

This document is the property of Worldwide Clinical Trials Inc. and may not be duplicated, copied, altered or removed from company without prior approval from Worldwide Quality Assurance or in compliance with Worldwide Standard Operating Procedures.

Worldwide Clinical Trials Controlled Quality Management Document		
 WORLDWIDE CLINICAL TRIALS	Sponsor:	Global Alliance for TB Drug Development
	Protocol Number:	TBAJ-876-CL001
STATISTICAL ANALYSIS PLAN – PHASE 1		

The effect of food on bioavailability of TBAJ-876 will be studied in a food-effect cohort comprised of two parallel groups, one fasting and the other fed. The fed group will enroll at least 10 subjects, which will yield complete data for at least 8 subjects if at most 2 fail to complete. For the fasted group, the data from the 6 subjects previously administered 100 mg TBAJ-876 in Cohort 4 (who have already completed the cohort) will be combined with data from 3 additional subjects to be enrolled in this fasted group. This will yield a complete data set for at least 8 subjects if at most 1 fails to complete. Thus, the total number of subjects planned is at least 60 to 70.

For Part 2, 39 subjects are planned to be enrolled. There are 3 cohorts planned. Cohort 1 with 12 subjects per cohort (9 to receive active drug and 3 to receive placebo). Cohort 2 with 13 subjects per cohort (9 to receive active drug and 4 to receive placebo), and Cohort 3 with 14 subjects per cohort (9 to receive active drug and 5 to receive placebo). All doses in Part 2 will be under fed conditions.

For Part 3, 30 subjects are planned to be enrolled. There are 3 groups planned with 10 subjects per group. All subjects will receive active drug under fasted or fed conditions.

Additional cohorts may be enrolled if it is deemed appropriate by the Sponsor to repeat a dose level, to study another dose level, or to increase cohort size (subject numbers).

The number of subjects selected for the study was based on the adequate number considered to provide sufficient safety data. This study has not been formally powered.

## 5 RANDOMIZATION

In Parts 1 and 2, each subject will receive an assigned treatment (active or placebo) based on the randomization schedule prepared by the unblinded statistician. The unblinded pharmacy staff will ensure compliance with the randomization schedule.

All subjects entering the Part 1 food-effect cohort will receive active drug (TBAJ-876 100 mg). In this food-effect cohort, new subjects will be enrolled in two parallel groups, one fasting (3 additional subjects) and the other fed (10 subjects).

For Part 3, all subjects will be randomly allocated to receive active drug under fasted or fed conditions.

QMD Ref: Worldwide-TMP-ST-006-4.0 Effective: 12Aug2019	Governing QMD: Worldwide-SOP-ST-001
Confidentiality Statement	

This document is the property of Worldwide Clinical Trials Inc. and may not be duplicated, copied, altered or removed from company without prior approval from Worldwide Quality Assurance or in compliance with Worldwide Standard Operating Procedures.

Worldwide Clinical Trials Controlled Quality Management Document		
 WORLDWIDE CLINICAL TRIALS	Sponsor:	Global Alliance for TB Drug Development
	Protocol Number:	TBAJ-876-CL001
STATISTICAL ANALYSIS PLAN – PHASE 1		

## 6 PLANNED ANALYSES

No statistical analysis plan (SAP) prepared in advance of the data can be definitive and the final Clinical Study Report (CSR) may contain additional tables or statistical tests if warranted by the data obtained. The justification for any such additional analyses will be fully documented in the final CSR.

### 6.1 Analysis Sets

Subjects excluded from the analysis sets and the reason for their exclusion will be listed.

#### 6.1.1 All Enrolled Subjects

Enrolled subjects include all subjects who have given informed consent to participate in the study.

#### 6.1.2 Randomized Set

The Randomized Set includes all subjects to whom a treatment was randomly assigned.

#### 6.1.3 Safety Analysis Set

The Safety Analysis Set includes all subjects who received any dose of study drug.

#### 6.1.4 PK Analysis Set

The PK Analysis Set includes all subjects with sufficient data to derive PK parameters.

## 6.2 Derived Data

This section describes the derivations required for statistical analysis. Unless otherwise stated, variables derived in the source data will not be re-calculated.

### 6.2.1 Age

Age at screening will be calculated in SAS as

$$\text{age} = \text{floor} ((\text{intck}(\text{'month'}, \text{birthdate}, \text{date}) - (\text{day}(\text{date}) < \text{day}(\text{birthdate}))) / 12)$$

QMD Ref: Worldwide-TMP-ST-006-4.0 Effective: 12Aug2019	Governing QMD: Worldwide-SOP-ST-001
Confidentiality Statement	

This document is the property of Worldwide Clinical Trials Inc. and may not be duplicated, copied, altered or removed from company without prior approval from Worldwide Quality Assurance or in compliance with Worldwide Standard Operating Procedures.

Worldwide Clinical Trials Controlled Quality Management Document		
 WORLDWIDE CLINICAL TRIALS	Sponsor:	Global Alliance for TB Drug Development
	Protocol Number:	TBAJ-876-CL001
STATISTICAL ANALYSIS PLAN – PHASE 1		

## 6.2.2 Race

Where more than one race category has been selected for a subject, these race categories will be combined into a single category labeled “Multiple Race” in the summary tables. The listings will reflect the original selected categories.

## 6.2.3 Baseline

Baseline is defined as the last non-missing value (either scheduled, unscheduled or repeat) before the subject receives the first (or single) dose of study drug in the relevant study part.

## 6.2.4 Early Withdrawal Assessments

Early withdrawal assessments will be tabulated with End of Study (EOS).

## 6.2.5 Study Day / Duration

Study day will be calculated as the number of days from first dose of study drug.

- date of event – date of first dose of study drug + 1, for events on or after first dose.
- date of event – date of first dose of study drug, for events before first dose.

Duration is calculated in hours as (event end date-time – event start date-time).

## 6.2.6 Conventions for Missing and Partial Dates

It is not expected that there will be any missing dates, however in the rare case that an AE start date or time is missing, and it is unclear whether the AE is treatment emergent or not then a conservative approach will be taken, and it will be assumed that the AE occurred after first dosing.

All dates presented in the individual subject listings will be as recorded on the Electronic Case Report Form (eCRF).

## 6.2.7 Exposure to Study Drug

For dosing in Part 2 MAD, exposure to study drug will be calculated as follows from the date of last dosing minus the first day of dosing + 1. The exposure calculation will not take into account breaks in therapy.

QMD Ref: Worldwide-TMP-ST-006-4.0 Effective: 12Aug2019	Governing QMD: Worldwide-SOP-ST-001
Confidentiality Statement	

This document is the property of Worldwide Clinical Trials Inc. and may not be duplicated, copied, altered or removed from company without prior approval from Worldwide Quality Assurance or in compliance with Worldwide Standard Operating Procedures.

Worldwide Clinical Trials Controlled Quality Management Document		
 WORLDWIDE CLINICAL TRIALS	Sponsor:	Global Alliance for TB Drug Development
	Protocol Number:	TBAJ-876-CL001
STATISTICAL ANALYSIS PLAN – PHASE 1		

## 6.2.8 Inexact Values

In the case where a safety laboratory variable is recorded as “> x”, “≥ x”, “< x” or “≤ x”, a value of x will be taken for analysis purposes.

## 6.2.9 Electrocardiogram Data

For ECG data recorded on continuous scales, if more than one value is recorded at a time point, the mean value rounded to the integer will be presented. For overall interpretation if more than one value is recorded, the most severe (worst case) of the respective readings will be taken.

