Three cohorts are planned. Cohort 1 with 12 subjects per cohort (9 to receive active drug and 3 to receive placebo), Cohort 2 with 13 subjects per cohort (9 to receive active drug and 4 to receive placebo), and Cohort 3 with 14 subjects per cohort (9 to receive active drug and 5 to receive placebo) to receive TBAJ-876 or matching placebo for 14 days, all under fed conditions.

For Cohorts 2 and 3, an additional ECG extraction will occur at 16 hours postdose on Day 1 and Day 14. For Cohort 3, all ECGs performed will be triplicate ECGs at each time point listed in the Schedule of Assessments.

Additional cohorts may be enrolled if deemed appropriate by the Sponsor to repeat a dose level or to study another dose level.

Part 3:

Three groups each consisting of 10 subjects are planned.

Test product, dosage, and mode of administration:

Part 1:

TBAJ-876 Oral Suspension, orally administered

Dose Level 1: 10 mg TBAJ-876

Dose Level 2: 25 mg TBAJ-876

Dose Level 3: 50 mg TBAJ-876

Dose Level 4 and food-effect cohort: 100 mg TBAJ-876

Dose Level 5: 200 mg TBAJ-876

Dose Level 6: 400 mg TBAJ-876

Dose Level 7: 800 mg TBAJ-876

Additional cohorts may be enrolled if deemed appropriate by the Sponsor to repeat a dose level or to study another dose level.

Part 2:

TBAJ-876 Oral Suspension, orally administered

Dose Level 1: 25 mg TBAJ-876

Dose Level 2: 75 mg TBAJ-876

Dose Level 3: TBD mg TBAJ-876

Doses may change based on what is learned from previous cohorts. Additional cohorts may be enrolled if deemed appropriate by the Sponsor to repeat a dose level or to study another dose level.

Part 3:

TBAJ-876 Tablets, orally administered

Group 1: 100 mg TBAJ-876 (1 x 100 mg tablet) under fasted conditions

Group 2: 100 mg TBAJ-876 (1 x 100 mg tablet) under fed conditions

Group 3: 100 mg TBAJ-876 (4 x 25 mg tablets) under fasted conditions

Control product, dosage, and mode of administration:

Placebo for TBAJ-876 Oral Suspension; orally administered

All levels (except Part 1 food-effect cohort and Part 3) = Matching dose of placebo for TBAJ-876 Oral Suspension

Criteria for evaluation:

Safety: Safety assessments will include physical examination (including heart murmurs), vital signs, electrocardiograms (ECGs), extensive cardiac monitoring including telemetry, adverse events (AEs),

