6.9.5 Electrocardiograms

For Part 1, triplicate ECGs will be completed at screening, Day -1, 48 hours, and Day 8 or early withdrawal only. All other time points will be single ECG readings within 15 minutes of time points on Table 15.

The predose ECG will be performed prior to the predose blood draw. If a subject experiences a postdose QTcF >500 msec or a change from baseline QTcF >60 msec, after repeat testing, additional ECGs should be recorded until normalization or return to baseline.

For Cohort 7, all ECGs will be triplicate at each time point. In addition, subjects in will have triplicate ECGs at 16 hours postdose.

For Part 2, triplicate ECGs will be completed at screening, Day -1, Day 15 or early withdrawal only. All other time points on Table 16 will be single ECG readings. ECGs

may be done within 2 hours prior to time of dosing and at 6 hours after dosing on Days 1, 2, 3, 8, 12, 14, and on Days 42, 63, 84, 105, and 126.

For Cohorts 2 and 3, an additional ECG extraction will occur at 16 hours postdose on Day 1 and Day 14. For Cohort 3, all ECGs performed will be triplicate ECGs at each time point listed in Table 16.

For Part 3, triplicate ECGs will be completed with 15 minutes at all timepoints on Table 17.

NOTE: Where possible, ECG extractions should be taken from the continuous 12-lead ECGs (Holter).

The predose ECG should be completed within 1 hour prior to the predose blood draw. If a subject experiences a postdose QTcF >500 ms with a change from baseline QTcF >60 ms, after repeat testing, the Principal Investigator should be notified, and additional ECGs should be recorded until normalization or return to baseline.

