#### 6.11.6 Electrocardiogram Data

Descriptive statistics for observed values and changes from baseline in the following ECG variables will be tabulated by treatment group at each visit:

- Heart rate (bpm)
- PR duration (ms)
- QRS duration (ms)
- RR interval (ms)
- QT interval (ms)
- QTc interval (ms)
- QTcB interval (ms) [Bazett's formula]
- QTcF interval (ms) [Fridericia's formula]

Shift tables in relation to the overall interpretation (Normal, Abnormal NCS, and Abnormal CS), from baseline to each follow-up visit will be presented. All ECG data, including details of any abnormalities, will be listed.

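### Overall ECG interpretation is scored by the worst replicate, but only the top-dose cohorts of Parts 1 and 2 are read in triplicate throughout, so dose columns are not like for like

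*SAP*

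**What the plan says.** SAP 6.2.9 has two rules for replicate ECGs. For continuous variables, "if more than one value is recorded at a time point, the mean value rounded to the integer will be presented". For the categorical reading, "For overall interpretation if more than one value is recorded, the most severe (worst case) of the respective readings will be taken". SAP 6.11.6 then plans the output: "Shift tables in relation to the overall interpretation (Normal, Abnormal NCS, and Abnormal CS), from baseline to each follow-up visit will be presented". Under SAP 6.3 these tables are laid out by treatment group, with one placebo column per part.

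Protocol 6.9.5 sets the number of readings:

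- Part 1 in general: "For Part 1, triplicate ECGs will be completed at screening, Day -1, 48 hours, and Day 8 or early withdrawal only". For the rest, "All other time points will be single ECG readings within 15 minutes of time points on Table 15".
- Part 1 Cohort 7: "For Cohort 7, all ECGs will be triplicate at each time point". The protocol synopsis gives its dose: "Dose Level 7: 800 mg TBAJ-876". The next highest is 400 mg.
- Part 2 in general: triplicates at screening, Day -1, and Day 15 or early withdrawal; single readings otherwise.
- Part 2 Cohort 3: "For Cohort 3, all ECGs performed will be triplicate ECGs at each time point listed in Table 16". Its dose is 200 mg in the SAP section 9 table titles, against 25 and 75 mg for Cohorts 1 and 2. The protocol synopsis and the SAP 6.3 labels still leave it to be determined.
- Part 3: triplicate at all time points in all three 100 mg groups, so the issue does not arise there.

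SAP 6.2.3 takes baseline as the last value before dosing. In the lower-dose cohorts that is a single Day 1 predose ECG; in Cohort 7 and Part 2 Cohort 3 it is a triplicate. Nothing in the SAP adjusts for the number of readings.

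**The concern.** A worst-of-replicates rule gives a subject read three times three chances to be called abnormal, and a subject read once one chance. Here the number of chances is tied to dose. Safety is the primary objective, cardiac muscle damage was seen in dogs, and the overall-interpretation shift is the only categorical summary of the safety ECGs that the SAP plans. SAP 6.11.6 has no QTc threshold table, and 6.11.7 only lists Holter start and stop data. A reader comparing columns could take a difference made by the reading schedule for an effect of the highest dose.

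Pooled placebo does not remove the difference. As planned, 2 of 14 placebo subjects in Part 1 and 5 of 12 in Part 2 are read in triplicate throughout, against all active subjects at the top dose.

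**Working it through.** The documents give no abnormal rate, replicate agreement or power figure here, so there is no stated number to reproduce. Let p be the chance that one reading is called abnormal with no drug effect; p and the correlation are assumptions. Abnormal NCS and Abnormal CS are counted together.

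**1. Post-dose abnormal share.** With independent readings, worst-of-three is w = 1 − (1 − p)³.

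| p | single | worst-of-three | ratio |
|---|---|---|---|
| 1% | 1.0% | 3.0% | 3.0 |
| 5% | 5.0% | 14.3% | 2.9 |
| 10% | 10.0% | 27.1% | 2.7 |
| 20% | 20.0% | 48.8% | 2.4 |

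For correlated readings, let the abnormal probability follow a Beta distribution with mean p and intraclass correlation ρ: a = p(1 − ρ)/ρ, b = (1 − p)(1 − ρ)/ρ. The chance that k readings are all normal is E(k), the product of (b + j)/(a + b + j) for j = 0 to k − 1. Worst-of-three is 1 − E(3). At p = 10% this is 20.8% at ρ = 0.3, 15.8% at 0.6 and 11.4% at 0.9: smaller as replicates agree, but always above 10%.

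Expected abnormal subjects per time point at p = 10%, independent: 6 × 0.10 = 0.6 against 6 × 0.271 = 1.6 for six active subjects (Cohort 7 size), and 9 × 0.10 = 0.9 against 9 × 0.271 = 2.4 for nine (Part 2 Cohort 3 size).

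**2. Pooled placebo at p = 10%.**

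- Part 2: (7 × 0.10 + 5w)/12 = 17.1% (independent), 14.5% (ρ = 0.3), 12.4% (ρ = 0.6).
- Part 1: (12 × 0.10 + 2w)/14 = 12.4% (independent).

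**3. Normal-to-Abnormal cell.** The planned output is a shift, so baseline matters. With independent readings, one at both times gives (1 − p)p and three at both times gives (1 − w)w. If abnormality is a persistent subject trait, so that predose and post-dose readings share the same correlation, these become E(1) − E(2) and E(3) − E(6).

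| p = 10% | one / one | three / three |
|---|---|---|
| independent | 9.0% | 19.8% |
| ρ = 0.3, persistent | 6.3% | 8.6% |
| ρ = 0.6, persistent | 3.6% | 3.7% |
| ρ = 0.7, persistent | 2.7% | 2.6% |

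If abnormality is instead transient (replicates at one time point agree, predose and post-dose do not), the comparator stays at 0.9 × 0.1 = 9.0%. The top cohort then has 0.792 × 0.208 = 16.5% at ρ = 0.3 and 0.842 × 0.158 = 13.3% at 0.6.

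**4. Rows where every cohort is triplicate post-dose.** At 48 h and Day 8 (Part 1) and Day 15 (Part 2) the post-dose readings match across cohorts. The lower cohorts, however, compare a single baseline with a worst-of-three: (1 − p)w = 0.9 × 0.271 = 24.4% if independent, and E(1) − E(4) = 14.3% at ρ = 0.3. One reading at both times would give 9.0% and 6.3%. In these rows it is the lower cohorts' own shifts that are inflated.

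**The case against.** The strongest reply is that the post-dose share is not what SAP 6.11.6 tabulates. The table is a shift, and worst-of-three also raises abnormal baselines in the top cohorts. That stands. Expected net shift there is zero, and the Normal-to-Abnormal excess disappears by a correlation of about 0.6 if abnormality persists within subjects. The protocol gives some reason to expect persistence: exclusion criterion 13 lets axis deviation, incomplete right bundle branch block and mild first-degree block pass as not clinically significant, and these would usually appear in every replicate and at baseline.

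Other points also stand. The rule operates only if each replicate's interpretation is recorded, and the documents do not show whether the case report form holds one per triplicate or three. The cohort stopping rule in protocol 3.2 uses QTcF, continuous ECG summaries use the mean, and all ECG data are listed. The table is descriptive in an unpowered study. For rare calls the excess is small: at p = 1%, about 0.12 of a subject in six (0.18 against 0.06).

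Worst-case scoring is also a defensible conservative choice in a first-in-human study. That supports keeping such a table, but not comparing columns that rest on different numbers of readings.

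A reader might infer that the tables build in a false dose-response, or that the ratios of 2.4 to 3.0 in step 1 apply to the shifts. The documents support neither. The artefact is confined to one cohort per part, is absent from the post-dose readings at 48 h, Day 8 and Day 15, and is smaller in the shift cell than in the post-dose share.

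**Conclusion.** The concern holds in a limited form. The rule and schedule are as quoted, and no SAP text corrects for them. With no drug effect, the top-dose column of Part 1 and of Part 2 has a higher expected post-dose share of abnormal ECGs than lower doses or pooled placebo, at time points where the other cohorts are read once and whenever replicates can disagree.

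The direction is firm. The size rests on an assumed single-reading rate and assumed agreement, and on each replicate's interpretation being recorded. The shift cell may be roughly doubled or not inflated at all, depending on how persistent abnormality is. The opposite distortion, in the lower cohorts at the all-triplicate rows, means that the bias changes from row to row of the same table. QTcF and the other continuous variables are not affected.

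**What to change.** In SAP 6.2.9 and 6.11.6:

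- Base comparison across dose groups on an overall-interpretation shift table that uses one pre-specified reading, such as the first, at baseline and at each time point in every cohort. The expected abnormal share with no drug effect is then p in every column.
- Keep the worst-of-replicates table as a conservative safety display. Label it with the number of readings per cohort and time point, and do not use it to compare doses except among subjects read in triplicate throughout.
- Keep every replicate in the listings.

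A majority-of-three rule applied only where triplicates exist would not serve. At p = 10% with independent readings it gives 3 × 0.1² × 0.9 + 0.1³ = 2.8% against 10%, which reverses the imbalance.

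Protocol 6.8 lists a triplicate ECG at the end-of-study visit, whereas 6.9.5 does not include that visit among its triplicate times. These passages must be reconciled so that the labels are right.

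The cost is one extra table and a short programming rule. An abnormality seen only in the second or third replicate does not appear in the one-reading table, but it remains in the worst-case table and the listings.

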## 6.2.10 Unscheduled Visits

Only scheduled post-baseline assessment values will be tabulated. Post-baseline repeat / unscheduled assessments will not be summarized, but these post-baseline assessments will be listed in the relevant appendices to the CSR.

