3.2 Stopping Rules for Cohorts for Participants Receiving Active Drug

If any of the cohort stopping rules are met, cohort dosing must be stopped to allow review of the data by the Sponsor and the Investigator. As with dose escalation review, the review of data here is also blinded except for review by the 2 experienced

individuals not directly involved in the study (see unblinding procedures; Section 6.2.6).

Rules for stopping dosing of a cohort include the following:

- a. One subject experiences one or more drug-related SAEs.
- b. Two or more subjects experience Grade 3 or 4 (per DMID) myalgia in combination with increase of CPK (at least 3 times the upper limit of the normal range [ULN] confirmed at 48 hours).
- c. Two or more subjects have a QTcF \geq 500 ms with an increase from baseline > 60 ms.
- d. Two or more subjects experience confirmed Grade 3 or 4 AEs (per DMID) in any one of the following laboratory parameters: alanine aminotransferase (ALT), aspartate aminotransferase (AST), alkaline phosphatase (ALP), amylase, or lipase.

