### 6.11.2 Laboratory Data

Descriptive statistics of the observed values and change from baseline (continuous data) will be presented by treatment group and visit for each hematology, serum chemistry, coagulation and urinalysis parameter. Change from baseline in categorical parameters will be presented in the natural order of the outcome where possible.

Each measurement (for continuous data and for categorical data where provided) will be classed as below, within, or above normal range, based on ranges supplied by the laboratory used. Shift tables in relation to the normal range from baseline to each follow-up visit will be presented.

All individual laboratory data, including serology, drug, alcohol and cotinine screening, pregnancy testing and FSH data will be listed, with a separate listing of any clinically significant laboratory measurements recorded throughout the study presented in Appendix 14.3.4 of the CSR.

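### Post-baseline repeat and unscheduled values are left out of the by-visit safety tables and no worst-post-baseline summary is planned, so a CPK, troponin I or QTcF peak seen only off schedule may reach no table

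*SAP*

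**What the plan says.** SAP 6.2.10 limits the tables: "Only scheduled post-baseline assessment values will be tabulated". It continues: "Post-baseline repeat / unscheduled assessments will not be summarized, but these post-baseline assessments will be listed in the relevant appendices to the CSR".

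Before dosing the rule is different. SAP 6.2.3 reads: "Baseline is defined as the last non-missing value (either scheduled, unscheduled or repeat) before the subject receives the first (or single) dose".

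The planned laboratory output is by visit. SAP 6.11.2 gives descriptive statistics by visit and adds: "Shift tables in relation to the normal range from baseline to each follow-up visit will be presented". SAP 6.11.3 and 6.11.6 follow the same pattern for vital signs and ECGs. The SAP also plans a separate listing of clinically significant laboratory values from the whole study (CSR 14.3.4) and TEAE tables by maximum DMID grade (Table 14.3.1.4).

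The protocol expects repeat measurements. Section 7.7 lets the investigator repeat a test to verify a result, Section 6.7 allows extra blood for that purpose, and Section 6.9.5 asks for further ECGs after a QTcF finding. Two of the four cohort stopping rules in Section 3.2 refer to confirmation: "increase of CPK (at least 3 times the upper limit of the normal range [ULN] confirmed at 48 hours" and "Two or more subjects experience confirmed Grade 3 or 4 AEs".

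**The concern.** Safety and tolerability are the primary objective. The leading nonclinical findings are skeletal muscle damage with very high CK in rats and cardiac muscle damage with raised troponin I in dogs (Protocol 1.3). Protocol 1.6 asks for both to be followed through biomarkers. These are measurements that an investigator would repeat between visits. If the highest value falls on such a sample, the by-visit tables show only the scheduled values around it, and no planned table gives each subject's worst value.

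**Working it through.** No sample-size or power figure bears on this point; both documents say that the study was not formally powered. The check follows an unscheduled post-baseline value through the planned outputs.

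**1. Where can the value appear?**

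| Output | Does it include the value? |
|---|---|
| By-visit statistics and shifts (Tables 14.3.6.1, 14.3.7.1 to 14.3.7.10) | No, by SAP 6.2.10 |
| Subject listings (16.2.8) | Yes |
| Listing of clinically significant laboratory values (14.3.4.1) | Only if judged clinically significant |
| AE tables (14.3.1.1 to 14.3.1.5) | Only if reported as an AE |
| Worst-post-baseline, DMID-grade laboratory or QTcF-category table | None planned |

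The AE tables are therefore the only summary it can reach.

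**2. When does it become an AE?** Protocol 7.7 makes every laboratory change of Grade 2 or higher an AE, and does not restrict this to scheduled samples.

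- ALT, AST, ALP, amylase and lipase have rows in Appendix 3. A Grade 2 or higher value is an AE whichever sample shows it.
- CPK and troponin I have no row. Protocol Table 14 then applies a general scale built on discomfort, limitation of activity and need for treatment. A symptom-free rise can be Grade 1 on that scale whatever its size. It is then an AE only if the investigator judges it clinically significant.
- QTcF has no row, and the automatic rule covers laboratory values and hypertension or hypotension only.

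The protocol itself expresses CPK as multiples of ULN: above 1.25 in exclusion criterion 9 and at least 3 in stopping rule b.

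**3. The four stopping rules**

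- Rule a, "One subject experiences one or more drug-related SAEs", needs no confirmatory value and is summarized under serious treatment-related TEAEs.
- Rule b joins Grade 3 or 4 myalgia to a raised CPK. The myalgia is an AE tabulated by grade. The confirming CPK is tabulated only if its sample was scheduled.
- Rule c (QTcF) does not ask for confirmation. Repeat ECGs are listed only.
- Rule d is defined on AEs, so its events enter the AE tables.

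So 2 of 4 rules ask for confirmation, and one of those two is fully carried by the AE tables.

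**4. Is a 48-hour confirmation off schedule?** The phrase in rule b can mean 48 hours after dosing or 48 hours after the first raised value.

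- Parts 1 and 3: 48 hours postdose is a scheduled laboratory time. On the second meaning, some confirmations still fall on schedule: Day 5 is 96 hours and 96 − 48 = 48; Day 7 is 144 hours and 144 − 96 = 48.
- Part 2: laboratory visits after check-in are Days 7, 14, 21, 42, 63, 84, 105 and 126, and the smallest gap is 7 days. Repeats 48 hours after Days 7 and 14 would fall on Days 9 and 16. Neither is a scheduled laboratory day, so such values would be untabulated.

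**5. Weight of one subject in a worst-value summary**

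- Most Part 1 dose groups: 1/6 = 17%.
- Part 1, 100 mg: fasted 6 + 3 = 9, so 1/9 = 11%; fed 1/10 = 10%.
- Part 2 active groups: 1/9 = 11%.
- Part 3 groups: 1/10 = 10%.

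These are shares in a summary that is not now planned. They are not changes to an existing by-visit cell, because an unscheduled value belongs to no visit.

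**The case against.** The case for leaving the SAP alone has real content.

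- The values are listed, and Grade 2 or higher laboratory changes are tabulated as AEs. A reader might infer that confirmatory values appear in no summary at all. The documents do not support that: rule d is itself an AE rule, and the AE tables carry its events by maximum grade.
- Stopping is decided during the trial, on data reviewed by the sponsor, the investigator and two unblinded individuals outside the study. A reader might infer that SAP 6.2.10 weakens the stopping rules. It does not touch them.
- A reader might also suppose that most rises fall between visits, or that the tables must look too clean. Neither is shown. Part 1 sampling is dense (6 and 48 hours, then Days 5, 7, 10, 14, 17, 21 and 28). An initial abnormality at a scheduled visit is tabulated even if its repeat is normal.
- Keeping repeats out of by-visit statistics is sound, because they are triggered by abnormal results. Letting a repeat set the baseline serves a different purpose and is not in itself inconsistent.
- The lack of DMID-grade laboratory tables and QTcF-category tables would remain even if repeats were tabulated.
- SAP Section 6 allows additional CSR tables, and Protocol 6.2.5 has the cardiac vendor present ECG data in aggregate, though its content is not described.

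All of this narrows the point. It does not supply a planned summary for an off-schedule peak in CPK, troponin I or QTcF. An option to add tables later is weaker than a derivation fixed in advance.

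**Conclusion.** The gap is real and limited to reporting. Following the SAP exactly, a CPK, troponin I or QTcF peak that occurs only on a repeat or unscheduled measurement may be found in listings alone. This rests on three conditions: the worst value is off schedule, no graded row in Appendix 3 forces an AE, and the investigator does not report the value as an AE. How often all three will hold cannot be estimated from the documents. When they do, one affected subject is 10% to 17% of a dose group. For the five enzymes in rule d the AE tables close the gap from Grade 2 upward. The change is a cheap improvement worth making in a trial whose primary objective is safety; nothing here calls the in-trial safety decisions into question.

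**What to change.** Keep scheduled-only values in the by-visit statistics and shifts. Add to SAP 6.2.10, 6.11.2 and 6.11.6 a worst-post-baseline summary per subject that uses all scheduled, repeat and unscheduled values:

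- by DMID grade for parameters with a row in Appendix 3;
- by multiples of ULN for CPK and troponin I, naming troponin I explicitly because Protocol 6.9.2 places it outside the four panels that SAP 6.11.2 summarizes;
- by QTcF category, stating whether the mean under SAP 6.2.9 or the single reading is used.

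Two protocol points need settling first. The QTcF limits differ: Section 3.2 has at least 500 ms together with a rise above 60 ms, while Section 6.9.5 has above 500 ms or a rise above 60 ms in one place and above 500 ms together with that rise in another. These passages must be reconciled before categories are taken from them. The protocol should also state from what time the 48-hour CPK confirmation is counted.

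The cost is one derived record per parameter, a few extra table rows, and the work of agreeing the categories. No extra data are collected.
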